z.r) Randomized, Efficacy Study -- Surgical Techniques/Interventions

Discuss the research design including but not limited to such issues as: probability of group assignment, potential for subject to be randomized to placebo group, use of control subjects, etc.

50% of patients will be randomized into the EU-PC and 50% into the APT intervention. It is equally likely that a participant will be randomized into either intervention. The RA will not know when consenting the subject if they will be in the active APT intervention or in the control group (EU-PC).

Inclusion Criteria:

Patients can participate in the study if they meet the following criteria: (1) have a documented diagnosis of dementia; (2) receive care from, BCM GMA, the BCM Alzheimer Center, or Kelsey-Seybold; (3) reside outside Nursing Home; (4) live within 40 miles of the Texas Medical Center; (5) have mild-to-moderate dementia; (6) have no history of aggression in the past month; (7) have an informal caregiver directly involved with them at least 8 hours a week who sees them at least twice a week; (8) speak English; and (9) report clinically significant pain, depression, or caregiver/PWD relationship difficulties (either self-report or caregiver proxy-report).

Exclusion Criteria:

Patients with advanced dementia will be excluded by 2 criteria: a) score of greater than 6 on the Functional Assessment Staging (FAST) scale; or b) inability to complete by phone the Memory Impairment Screen--Telephone Version (MIS-T) or Philadelphia Geriatric Pain Intensity Scale. PWD will also be excluded if they have been aggressive in the past month; we will administer the aggression subscale of the Cohen-Mansfield Agitation Inventory (CMAI).

F2. Procedure

Our patient identification and recruitment procedures are based on our prior studies of PWD. The key initial criterion for study eligibility for patients is having a dementia diagnosis. The research team will partner with participating sites through 3 recruitment mechanisms to identify PWD: (1) direct provider referral (2) patient self-referral and (3) partial HIPAA-waiver-approved, database-generated lists of patients meeting geographical and selected ICD-9 codes from the 046, 290, 291, 292, 294, 331 and 333 series (or corresponding ICD-10 codes).

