In general, the primary source of missing data will be through participant attrition. We anticipate a low attrition rate (10%) based on our prior work. As described below, we will use analytic techniques (eg, hierarchical linear models) that are robust to violation of missing-data assumptions (ie, ¿missing completely at random¿). To reduce the possibility of bias in missing data, where possible, we will incorporate information from secondary sources for participants with missing data from attrition to try to ascertain whether they differ in important ways from other study participants. We will use X2 tests to determine whether there are differences in attrition between the 2 study arms. Prior to testing hypotheses, we will compare baseline demographic and clinical variables in APT and EU-PC with X2 and independent sample t-tests. Variables with p values < .25 in these univariate tests will be included as covariates in all subsequent multivariate models107 or as propensity scores.

Primary Hypothesis: APT will result in lower 1-year incidence of aggression than EU-PC. We will use negative binomial regression models to estimate the difference between our intervention and the control group in the rate of aggressive behavior at the 1-year follow-up period. For participants who drop out of the study, their time until study attrition will be used as their exposure period. Statistical significance will be determined using the X2 statistic associated with the parameter estimate for group membership. Baseline demographic and clinical variables that differ between groups in univariate tests will be included as covariates or propensity scores.

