Secondary Hypotheses 1: APT will result in greater reduction in aggression-related outcomes (nursing home placement, caregiver burden, positive aspects of caregiving, and behavior problems) over the 1-year assessment period than EU-PC. We will separately identify between-group (APT vs. EU-PC) differences in change over the 1-year follow-up period for injuries to PWD or others, caregiver burden, and nursing home placement, using a hierarchical linear modeling approach to repeated-measure modeling. These mixed models will maximize participant data by allowing us to account for various lengths of follow-up for each participant, as well as for missing observations (other than attrition). Conditional models will contain fixed terms for the intercept, treatment group (APT or EU-PC), time period (baseline; 3, 6, or 12 months), treatment group by time period interaction, and any previously identified variables that differ between treatment groups. Modeled random effects will include between-patient variation in baseline scores (i.e., the intercept where baseline assessments are scored 0) and variation in the slopes over time. In other words, we will model and attempt to explain variance between treatment groups for both baseline outcomes and overall change over time in outcomes. Given the 4 time points, the focus will initially be on linear patterns of change, although we will evaluate the relative fit of a quadratic or cubic pattern of change, using the likelihood ratio test. These analyses will allow us to examine the immediate impact of treatment, as well as retention, improvement, or decay in outcomes across the 12-month follow-up period.

Reduction in risk of nursing-home admission will be evaluated using a Cox proportional hazards model to test for between-treatment group differences. Similar to the approach we used for Hypothesis 1 to test for differences in onset of aggression, we will first estimate the unadjusted differences between groups, followed by estimates incorporating all identified covariates.

Secondary Hypothesis 2: APT will result in greater decreases in pain severity and pain-related features (low pleasant-activity levels, poor quality of caregiver-PWD relationship and depressive symptoms) than EU-PC over the 1-year follow-up period. These analyses will be conducted using the same approaches described for secondary Hypothesis 1.

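### Nursing-home placement is put into a linear model of change with a baseline variance that eligibility makes zero, and is then tested again by Cox with no statement of which result decides

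*Combined protocol and SAP*

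**What the plan says.** Section F1 (Inclusion Criteria) requires that the person with dementia "3) reside outside Nursing Home".

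Section G1, Secondary Hypotheses 1, then lists the outcomes whose change over the year will be compared between arms: "injuries to PWD or others, caregiver burden, and nursing home placement, using a hierarchical linear modeling approach to repeated-measure modeling". The random effects of that model are "between-patient variation in baseline scores (i.e., the intercept where baseline assessments are scored 0) and variation in the slopes over time". The fixed part has group, time (0, 3, 6, 12 months) and their interaction. Linear change is considered first.

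The next paragraph returns to placement: "Reduction in risk of nursing-home admission will be evaluated using a Cox proportional hazards model to test for between-treatment group differences". It justifies the method by a cross-reference: "Similar to the approach we used for Hypothesis 1 to test for differences in onset of aggression". On adjustment, the order given for the Cox estimates is this: "we will first estimate the unadjusted differences between groups, followed by estimates incorporating all identified covariates".

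The primary-hypothesis paragraph to which this seems to point reads: "We will use negative binomial regression models to estimate the difference between our intervention and the control group in the rate of aggressive behavior". Under Attrition Rates and Missing Data, baseline variables with p below .25 "will be included as covariates in all subsequent multivariate models107 or as propensity scores".

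The outcome lists differ:

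- **Section D, objective 2:** injuries, caregiver burden (twice), placement, positive aspects of caregiving, behavior problems.
- **Hypothesis sentence:** the same without injuries.
- **Linear-model sentence:** injuries, burden and placement only.

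**The concern.** Placement is a one-way 0/1 event that nobody can have had at entry. A Gaussian model of change from a varying baseline does not describe it, and one of the two planned random effects has nothing to represent. The analyst will have to alter the model, and the plan does not say how. The choice affects the standard error of the group-by-time slope.

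The same outcome also has a second, better suited test by Cox. If one is significant and the other is not, no sentence says which is the finding.

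**Working it through.** The plan states no event rate, event count or power for placement, so there is no figure to reproduce.

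**Inputs.** From the plan: visits at 0, 3, 6 and 12 months; 220 dyads randomised 1:1, so 110 per arm. Assumed: control placement by 12 months of 5%, 10% or 20%; constant hazard; a placed person stays counted as placed; exact admission dates for Cox; no dropout (the plan expects about 10%); hazard ratio 0.5 where there is an effect; two-sided 0.05.

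**Design constants.** Σt = 21 and Σt² = 189, so Sxx = 189 − 21²/4 = 78.75. For the straight line fitted to each person, with residual variance s², the error variance is s² × 189/(4 × 78.75) = 0.60 s² for the intercept and s²/78.75 for the slope.

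**Why the baseline variance fails, at 10% placement under the null.** A person never placed contributes zeros. The others follow one of three patterns:

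| Placed in months | Probability | Slope | Intercept | SSE | Σty/√189 |
|---|---|---|---|---|---|
| 0-3 | 1 − 0.9^0.25 = 0.0260 | 0.0667 | 0.40 | 0.400 | 1.5275 |
| 3-6 | 0.9^0.25 − 0.9^0.5 = 0.0253 | 0.0952 | 0.00 | 0.286 | 1.3093 |
| 6-12 | 0.9^0.5 − 0.9 = 0.0487 | 0.0857 | −0.20 | 0.171 | 0.8729 |

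- Var(intercept) ≈ 0.0260 × 0.16 + 0.0487 × 0.04 = 0.0061.
- Mean SSE = 0.0260 × 0.400 + 0.0253 × 0.286 + 0.0487 × 0.171 = 0.0260. On 2 df per person, s² = 0.0130.
- Baseline variance = 0.0061 − 0.60 × 0.0130 = **−0.0017**.

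The expected estimate is negative. The fitted intercepts vary only because a straight line is forced through a step.

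**What dropping it does.** With a random slope only, s² pools the intercept scatter with the residuals: (218 × 0.0061/0.60 + 220 × 0.0260)/658 ≈ 0.0121. The variance of Σty/√189 is 0.1412 − 0.1154² = 0.1279. The model-based slope variance is (0.1279 − 0.0121)/189 + 0.0121/78.75 = 0.00077. The actual slope variance is 0.000703 − 0.00832² = 0.00063. The standard error is too large by about √(0.00077/0.00063) ≈ 1.10, so the test is conservative: 2 × [1 − Φ(1.96 × 1.10)] ≈ 3%.

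**Simulation.** Cox is represented by its score (log-rank) test. A separate check run of 10,000 trials per setting is in brackets.

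| Assumed control placement | 5% | 10% | 20% |
|---|---|---|---|
| Null: baseline variance ≤ 0 | 91% (89%) | 96% (96%) | 99% (99%) |
| Null: slope test rejects, unconstrained | 4.7% (4.9%) | 5.1% (4.7%) | 4.8% (5.2%) |
| Null: slope test rejects, intercept variance dropped | 3.8% (3.4%) | 3.2% (3.0%) | 2.1% (3.1%) |
| HR 0.5: power, intercept variance dropped | 11% (11%) | 19% (21%) | 40% (41%) |
| HR 0.5: power, Cox | 15% (14%) | 27% (28%) | 50% (51%) |
| HR 0.5: verdicts differ, unconstrained | 2.0% (1.6%) | 3.7% (4.0%) | 5.3% (5.1%) |
| HR 0.5: verdicts differ, intercept variance dropped | (5.5%) | (7.6%) | (10.4%) |

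For the last row, a shorter run of 2,000 trials gave 5.4%, 6.7% and 12.6%, so the top of that range is best read as roughly one trial in ten.

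**False positives if either test may count.** In the check run this was 5.3%, 5.4% and 6.1% with the unconstrained fit and 5.1%, 5.0% and 5.3% with the intercept variance dropped. At 198 dyads the unconstrained figures were 4.6%, 5.6% and 6.6%. The two tests are highly correlated.

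**The case against.** The best defence is that Cox is readable as the intended test. It has its own paragraph, Section D names it among the methods, and no other outcome is assigned to it. The mention of placement in the linear-model sentence then looks like a drafting overlap. That is probably right and is why the fix is small. It does not remove the mention, and no sentence ranks the two results.

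Four stronger readings are tempting, and the documents do not support them:

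- **The linear test is invalid or inflates false positives.** The calculations show a size near or below 5%. The loss is power and clarity.
- **There are three rival results, counting unadjusted and adjusted Cox.** Reporting unadjusted and then adjusted estimates is ordinary, and the covariate rule in G1 points to the adjusted one. Its choice between covariates and propensity scores is a plan-wide matter.
- **Two hypothesised outcomes have no analysis, and the plan predicts harm to caregivers.** The model text sits directly under a hypothesis naming positive aspects of caregiving and behavior problems, and no other model is offered for them. Speaking of a reduction in positive aspects is loose wording. No one-sided test is stated, so no estimate or p-value changes.
- **Injuries need a different model.** The documents do not say how injuries are recorded, so this cannot be judged.

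**Conclusion.** The point holds for nursing-home placement. The planned baseline variance cannot be estimated for an outcome that is zero for everyone at entry, and the same outcome has a second test with no stated precedence. That much follows from the text alone.

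The size is modest and depends on how the failed variance is handled, which the plan leaves open. Dropping it gives a conservative test with roughly 4 to 10 percentage points less power than Cox, and verdicts that differ in about 5-10% of trials. Leaving the fit unconstrained gives about 2-6%. These figures rest on the assumed placement rates, hazard ratio, exact admission dates and complete follow-up. The primary hypothesis is not affected. The list mismatches, the direction word and the cross-reference are editorial.

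**What to change.** In Section G1, Secondary Hypotheses 1, delete nursing-home placement from the linear-model sentence, make Cox its only test, and state that the adjusted estimate decides, in line with the covariate rule earlier in G1. The unadjusted estimate can still be reported.

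In the same edit, as minor wording:

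- Name caregiver burden, positive aspects of caregiving and behavior problems as linear-model outcomes.
- Use one outcome list in Section D, the hypothesis and the analysis text.
- State the favourable direction for positive aspects of caregiving, after checking how the scale is scored.
- Correct the pointer to an analysis of the onset of aggression. The primary-hypothesis paragraph describes a negative binomial model of a rate, with no onset analysis and no unadjusted-first step.

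The cost is a few sentences and the loss of one redundant test. No data collection changes, but the wording should be checked against how admission dates are recorded, which the documents do not say.

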We plan to use the information collected on the screening telephone call as research data for the following reasons: 1) We will use the information gathered to determine the reasons potential subjects did not want to participate in the study or did not qualify for the study, to aid in the design of future research targeting this population. 2) Some of the questions asked at screening are also needed to characterize participants that enroll in the study. To reduce study burden, we will not repeat these questions after written informed consent is obtained.

Participants who screen eligible during the telephone assessment and sign consent documents will proceed to baseline. Eligible participants will be randomly assigned to intervention groups (APT or EU-PC) immediately following baseline evaluation based on random numbers generated in SAS PROC PLAN.

Assessments. Assessments will be done at baseline and 3, 6, and 12 months and will consist of a measure of demographic information and validated instruments. They will be administered by independent evaluators (IEs) blinded to random assignment. The CLOX Drawing Test (see Section S) will be administered in-person at baseline to a subset of 100 consecutively enrolled subjects; it should take less than ten minutes to complete. Prior to the assessment, instructions will be given to each subject in terms of what the measure is testing (i.e. ¿I will be assessing your ability to draw a clock¿). The remainder of the assessments will be administered by telephone. An unblinded RA will notify the PCP or referring MD of patients who have been identified as having clinically significant pain, depression, or aggression at baseline or on any of the follow-up calls (see Documentation and Reporting Guidelines attached in Section S).

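### The mixed models for the continuous secondary outcomes let the arms differ at baseline although randomisation follows baseline; a common baseline mean would add precision at no cost

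*Combined protocol and SAP*

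**What the plan says.** Section G1, under Secondary Hypotheses 1, sets out a hierarchical linear model for repeated measures. Its fixed part is described as "Conditional models will contain fixed terms for the intercept, treatment group (APT or EU-PC), time period (baseline; 3, 6, or 12 months"), followed by "treatment group by time period interaction, and any previously identified variables that differ between treatment groups". Baseline is therefore a response, and each arm has its own mean there.

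The random part has an intercept and a slope: "Modeled random effects will include between-patient variation in baseline scores (i.e., the intercept where baseline assessments are scored 0) and variation in the slopes". The next sentence restates this loosely: "we will model and attempt to explain variance between treatment groups for both baseline outcomes and overall change over time in outcomes". On the shape of the time effect, "Given the 4 time points, the focus will initially be on linear patterns of change", with quadratic and cubic terms tried afterwards.

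Secondary Hypothesis 2 adds nothing new: "These analyses will be conducted using the same approaches described for secondary Hypothesis 1". Section F2 fixes the order of events: "Eligible participants will be randomly assigned to intervention groups (APT or EU-PC) immediately following baseline evaluation". The only adjustment for baseline variables is the general rule in Section G1: "Variables with p values < .25 in these univariate tests will be included as covariates in all subsequent multivariate models107". Nowhere is a common baseline mean, or prespecified adjustment for the baseline score, laid down.

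**The concern.** With baseline coded as time 0, the group term is the difference between arms before treatment. Allocation had not happened when those scores were taken, so the true difference is zero and any observed difference is chance. The group-by-time term nevertheless measures each arm from its own estimated baseline, so the chance difference is subtracted at full weight. A common baseline mean removes it only as far as baseline predicts follow-up, which is the efficient amount.

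At stake is the width of the confidence intervals for caregiver burden, positive aspects of caregiving, behaviour problems, pain, pleasant activities, relationship quality and depression. The modelling paragraph itself lists only burden among these. I read it as covering all the continuous scales named in the two hypotheses.

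**Working it through.** **Inputs.** From the documents: visits at 0, 3, 6 and 12 months, 1:1 allocation, random intercept and slope, linear change first. Not in the documents: any correlation, intraclass correlation, SD or slope variance for these outcomes. Those values below are assumptions. With complete data the number per arm cancels from every ratio.

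The plan states no precision or power for these models, so there is no figure to reproduce. Its only power figures (97% and 80%, N = 100) belong to the executive-function regressions. They reproduce at 96.95% and 79.96% but do not bear on this point.

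**1. One visit, random intercept only** (equal variances, correlation rho). In units of 2 x sigma^2 / n per arm:

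- arms free at baseline: 2(1 - rho)
- common baseline mean: 1 - rho^2
- ratio: (1 + rho)/2, so the share of variance saved is (1 - rho)/2

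| rho (assumed) | free | common | variance saved | SE saved, 1 - sqrt((1 + rho)/2) |
|---|---|---|---|---|
| 0.3 | 1.40 | 0.91 | 35% | 19% |
| 0.5 | 1.00 | 0.75 | 25% | 13% |
| 0.7 | 0.60 | 0.51 | 15% | 8% |

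A simulation with 99 dyads per arm (220 less 10%, halved) and 1,500 runs gave 22.6% at rho 0.5 (theory 25%) and 12.9% at rho 0.75 (theory 12.5%).

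**2. The planned linear model.** Take time in years (0, 0.25, 0.5, 1) and baseline variance 1. Let g0 be the intercept variance, g1 the slope variance, s = 1 - g0 the residual variance, and g01 = corr x sqrt(g0 x g1).

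Sum of t = 1.75 and sum of t^2 = 1.3125, so the determinant is 4 x 1.3125 - 1.75^2 = 2.1875. The inverse of Z'Z has entries 0.6 (intercept), -0.8 (off-diagonal) and 1.8286 (slope). Within one arm, n times the covariance of the estimated intercept and slope is then:

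- c11 = g0 + 0.6s
- c12 = g01 - 0.8s
- c22 = g1 + 1.8286s

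With free baselines the slope contrast has variance 2 x c22 / n. With equal baselines it is 2 x (c22 - c12^2/c11) / n. The share saved is c12^2 / (c11 x c22). This is a squared correlation, so it cannot be negative. It vanishes when g01 = 0.8s.

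| g0 | g1 | corr | c12^2 / (c11 x c22) | variance saved | implied 0-12 month correlation |
|---|---|---|---|---|---|
| 0.3 | 0 | - | 0.3136 / (0.72 x 1.2800) | 34.0% | 0.30 |
| 0.5 | 0 | - | 0.1600 / (0.80 x 0.9143) | 21.9% | 0.50 |
| 0.7 | 0 | - | 0.0576 / (0.88 x 0.5486) | 11.9% | 0.70 |
| 0.5 | 0.25 | -0.3 | 0.2561 / (0.80 x 1.1643) | 27.5% | 0.39 |
| 0.7 | 0.21 | 0 | 0.0576 / (0.88 x 0.7586) | 8.6% | 0.64 |
| 0.7 | 0.21 | +0.3 | 0.0156 / (0.88 x 0.7586) | 2.3% | 0.68 |
| 0.75 | 0.50 | +0.3 | 0.0003 / (0.90 x 0.9571) | 0.0% | 0.68 |

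The last column is (g0 + g01) / sqrt(g0 + g1 + 2 x g01 + s). Rows with almost the same 0-12 month correlation (0.68 to 0.70) give anything from 0.0% to 11.9%, so that correlation does not settle the gain. Over g0 from 0.5 to 0.75, g1 from 0 to 0.5 and corr from -0.3 to 0.3, the range is 0% to 27.5%.

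**3. Does the p < .25 rule recover the loss?** No. A baseline score entered as a main effect shifts all four responses of a dyad by the same amount and cancels from change. In three simulated complete data sets (random intercept, categorical time), adding it left the group-by-time estimate and its standard error unchanged.

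**The case against.** The strongest reply is that this is a conventional growth model. Under randomisation it is unbiased and its type I error is intact; the affected analyses are secondary; and the gain may be negligible. All of that stands. A reader might infer from the free baseline term that the planned treatment comparison is biased or invalid. It is not; only efficiency is in question.

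A reader might also infer a fixed loss, such as at least 12% of the variance, or turn it into power or extra dyads. The documents do not support this. They give no correlation or variance components and no power for these outcomes, and the random-slope rows above show gains well below 12% under plausible values.

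Thirdly, a reader might take "we will model and attempt to explain variance between treatment groups for both baseline outcomes and overall change over time in outcomes" as a declared aim to explain a baseline difference between arms. The sentence directly follows the definition of the random intercept and slope and paraphrases it. It is better read as loose wording about variation between patients.

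What remains after these concessions is that the group term at time 0 has a known true value of zero, estimating it cannot help if the model is correct, and no other provision recovers the lost precision.

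**Conclusion.** The point holds as a free improvement, not as the correction of an error. For the continuous scale scores in Secondary Hypotheses 1 and 2, a common baseline mean would save (1 - rho)/2 of the variance of a single-visit contrast under a random intercept. Under the planned linear random-intercept-and-slope model it would save from near 0% to above 25%. Every figure rests on assumed variance components, complete data and a correctly specified model. That the saving is not negative rests only on the model being correct and on baseline preceding allocation, as Section F2 states.

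The point does not reach injuries or nursing-home placement, since patients must live outside a nursing home at entry and these are not scale scores with an informative baseline. Nor does it reach the Cox model or the primary negative binomial analysis.

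**What to change.** For the continuous outcomes listed above, remove the treatment-group main effect and keep time and group-by-time, so that both arms share one baseline mean (a constrained longitudinal model). If quadratic or cubic time is adopted, carry the matching group-by-time terms and still no group main effect.

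A closely related alternative is to model the 3-, 6- and 12-month scores with the baseline score as a prespecified covariate. It is not identical: it leaves three response times, excludes dyads with no follow-up score, and needs the random-effects part restated because the time-0 intercept goes. Choose one in advance.

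Reword the sentence on explaining variance so that it refers to differences between patients in starting level and rate of change, not between arms. State that injuries, nursing-home placement and the Cox model keep their own specification.

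The cost is one line of model specification and one reworded sentence, fixed in writing before any unblinded analysis. No new data or visits are needed.
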